A sample of up to 46 participants from the Baton Rouge, LA area will be enrolled. Due to the prolonged baseline assessment, enrollment is defined as having successfully completed the baseline assessments and having been randomized. Thus, more than 46 participants may begin the baseline period. We will enroll 46 participants. We anticipate ~10% attrition post-enrollment for about 20-21 completers per group and we are adequately powered with anticipated attrition.

Inclusion and Exclusion Criteria

- Inclusion criteria include:
 - Male or female, age 18-62 years
 - Body mass index (BMI) 18.5 – 50 kg/m², based on self-reported height and weight
 - Ownership of an iPhone, which the participant is willing to use for the study
 - Access to Apple ID, password, and email address and willing to use them in the course of the study
 - Performs a majority of household food shopping and preparation
 - If children are present in household, all children are between 6-18 years
 - Able to meet the schedule demands for the study
- Exclusion criteria include:
 - Not able to use an iPhone
 - Refusal or unable to use the smartphone app to collect data in free-living conditions
 - Households that purchase groceries less than 1 time per week
 - More than 2 children living in the household
 - Pennington Biomedical Research Center employee
 - Unwilling to sign consent to use web screener questions for data set and analysis.

Recruitment

Participant recruitment will be completed by Pennington Biomedical's recruitment core. Because most FV subsidy policies and programs target populations receiving SNAP, we will include recruitment at local food pantries to ensure an oversampling of participants who are likely SNAP eligible or recipients (target ~20% of participants). During the recruitment Web Screener, we will ask the participants the following 6 Food Insecurity screening questions:

1. In the last 12 months, did you ever eat less than you felt you should because there wasn't enough money for food?
--

2. In the last 12 months, were you ever hungry but didn't eat because you couldn't afford enough food?
--

3. In the last 12 months, did you ever cut the size of your meals or skip meals because there wasn't enough money for food?
4. In the last 12 months have you or other members of your household made a statement like, "The food that I bought just didn't last, and I didn't have money to get more."

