-8*	Visit 1 (~3 hours)	Attend training @ PBRC to: 
 • Provide informed consent. • Measure height weight and BMI. • Complete Baseline Survey (demographics, including SNAP eligibility assessment, socioeconomic variables), FV Preferences Survey, and Household Needs Survey (self-reported demographics, allergies, intolerances, and restrictions for household members). If desired or deemed necessary by the participant or the PBRC employee conducting the lab visit, surveys may be done after the appointment via REDCap. • Learn how to conduct household FV inventory. • Install and learn how to use the FoodImage app. 	
-8*	Day of* V1	Conduct a video home inventory of all Fruits & Vegetables (fresh, frozen, or otherwise preserved) via Microsoft Teams Call with study staff member.	
-7 - -1*	Week* following V1	Baseline Data Collection Use FoodImage to record food acquisition (Shop), food prep (Prep), intake (Eat) and waste (Toss). 
 • For approximately 3 (24 hour) days (ideally including 1 weekend date) use FoodImage to record all food acquisition (Shop), food prep (Prep), intake (Eat) and waste (Toss). 	
0	Visit 2 ~ +7* days from V1 (~ 3 hours)	Treatment Group Food Waste & Substitution 
 • Receive fruit and vegetable box. • Lifestyle Interview • Begin Intervention 	Control Group Stress Management 
 • Receive fruit and vegetable box. • Lifestyle Interview • Begin Intervention
0-7*	Week* following V2	Interventionist will check in with ppt goals and will send group specific nudges via participant's preferred form of communication between V2 and V3.	

0-35*	Ongoing until end of study	Use FoodImage to record food acquisition (Shop) & food waste from storage clean outs (Toss); continue interacting with PBRC staff on respective interventions.
8*	Visit 3 ~ +7* days from V2 (~ 2 hours)	Visit PBRC to receive free box of FV and receive follow up intervention/reinforcement.
8-15*	Week* following V3	Interventionist will check in with ppt goals and will send group specific nudges via participant's preferred form of communication between V3 and V4.
16*	Visit 4 ~ +7* days from V3 (~ 2 hours)	Visit PBRC to receive free box of FV and receive follow up intervention/reinforcement.

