 - b. FPED values, i.e. serving size, for food intake and consumption of FV including FV inventory, total FV acquisition, and total FV intake
 - c. Quantify baseline diet quality (i.e. food intake as assessed by the HEI)
- 2) Determine how the smart intervention altered:
 - a. Mass (grams), energy (kcal), and macronutrients (g and kcal) for household food waste levels, food purchasing patterns, food intake, and consumption of FV including FV inventory, total FV acquisition, and total FV intake
 - b. FPED values, i.e. serving size, for food intake and consumption of FV including FV inventory, total FV acquisition, and total FV intake
 - c. Quantify diet quality (i.e. food intake as assessed by the HEI)
 - d. Acquisition and intake of non-FV foods
 - e. The percent of household food waste that was FV

Secondary analysis objectives include assessing the demographic (e.g., age, education), household (SNAP eligibility, household size, beginning food inventories), and attitudinal factors (e.g., frugality, health and environmental consciousness) related to the primary analysis targets.

Power analysis

Power analysis was conducted for change in the primary outcome variable (grams [g] of food waste) from baseline to the end of the intervention to detect significant differences between treatment and control groups. Following the methods of our previous study, waste data will be summarized and analyzed by aggregating across measurement days. Based on weekly data from our previous study, the participants in the group receiving a smart food waste reduction intervention reduced their waste at meals by 331 g while the control group only reduced their waste by 33 g (298 g group difference), while the pooled standard deviation of the change in food waste between the control and treatment groups was 295 g, yielding an effect size of 1.01. The power to detect an effect size of 1.01 is 0.92 if there is no attrition (23 per group) and is 0.88 if attrition exceeds the 10% expectation (20 per group or 13% attrition). Given the power analysis is based upon an RCT that did not involve the provision of free FV, we expect effect sizes to be larger in the proposed study due to the presence of free FV, yielding even higher power than projected above.

Provisions to Monitor the Data to Ensure the Safety of Subjects

Adverse events will be monitored at each intervention visit. The PI and his co-investigators will review all data continuously to ensure the safety of each subject.

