Withdrawal of Subjects

Subjects may be withdrawn from the study if he/she misses study visits and will be notified of their withdrawal via telephone or mail. If a subject voluntarily withdraws from the study, no additional data will be collected and they will be considered dropouts in the study.

Risks to Subjects

This study involves no greater than minimal risk. The main risk is breach of confidentiality, and the PBRC team will work to minimize this during data collection, handling, and analysis.

Potential Benefits to Subjects

Participants may benefit by increased awareness of their food waste behaviors.

Setting

All research procedures will be conducted at PBRC and in participants' natural environment.

Resources Available

PBRC has all the necessary equipment needed to undertake and execute the proposed research project successfully. All investigators and staff have offices or cubicles. Investigator offices are each equipped with a desk, chair, filing cabinets and shelves, telephone with voice mail, printer, and access to a photocopier and fax. Computers are equipped with software for statistics, data management, and word processing, and computers are connected to the PBRC mainframe with internet access and email access through Outlook Express. Information Technology (IT) provides full technical support to all members of the faculty and staff. PBRC has all the

technological equipment and staff needed to conduct the present study. These information technologies assure efficient data handling and optimal communication among the investigators and the team.

Compensation

Participants will be compensated \$100 for successful completion of week 1 and \$165 for successful completion of the remaining 21 days (max compensation = \$265). Participants will also receive a free fresh seasonal FV box once per week during the final 21 days.

Confidentiality and Provisions to Protect the Privacy Interests of Subjects

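### Randomised participants may be withdrawn for missed visits, which can discard obtainable outcome data and leave the primary comparison to those who kept attending

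*Combined protocol and SAP*

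**What the plan says.** - **Withdrawal for missed visits** (Withdrawal of Subjects): "Subjects may be withdrawn from the study if he/she misses study visits". The section gives no number of visits, no criterion and no decision-maker. It does not say whether outcome data are still sought afterwards.
- **Voluntary withdrawal** (same section): "If a subject voluntarily withdraws from the study, no additional data will be collected and they will be considered dropouts in the study". This sentence concerns participants who choose to leave.
- **Timing of randomisation** (Participants; Procedures): "enrollment is defined as having successfully completed the baseline assessments and having been randomized". Randomisation is at Visit 2, so a missed Visit 3, 4 or 5 is a post-randomisation event.
- **Content of Visits 3 and 4** (Schedule of Procedures): "Visit PBRC to receive free box of FV and receive follow up intervention/reinforcement". No outcome measurement is listed at either visit.
- **Primary outcome** (Power analysis): "change in the primary outcome variable (grams [g] of food waste) from baseline to the end of the intervention". Follow-up data come from about 3 days of home recording with the app in the week after Visit 4. The closing fruit and vegetable inventory is a video call the day before Visit 5 (Procedures; Schedule of Procedures).
- **Attrition** (Participants): "We anticipate ~10% attrition post-enrollment for about 20-21 completers per group and we are adequately powered with anticipated attrition". The Power analysis section carries this through as 20 per group, or 13% attrition.
- **Not stated anywhere:** an analysis population, an as-randomised principle, a missing-data method or a sensitivity analysis.

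**The concern.** The rule lets attendance after randomisation decide who stays in the study, although attendance at Visits 3 and 4 is not needed to measure the primary outcome. A household that misses one of those visits can still record its food waste at home and take the inventory call. If it is withdrawn from the study, which most naturally means that follow-up also ends, obtainable outcome data are lost.

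Missed visits are also missed sessions of the assigned intervention: waste coaching in one arm, stress coaching in the other. The reasons for missing them, and how those reasons relate to food waste, need not be the same in both arms. With no named analysis set, the comparison may fall back on those with follow-up data. Randomisation no longer fully protects such a comparison, and at 23 per arm two or three households carry weight. The protocol does not say who decides on withdrawal or whether that person would be unaware of the arm.

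**Working it through.** **1. Can the outcome be obtained after a missed visit?**

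| Event | Where | Needed for the primary outcome? |
|---|---|---|
| Visit 3, Visit 4 | Centre; box and coaching | No |
| Follow-up recording, about 3 days, week after Visit 4 | Home, app | Yes |
| Closing inventory, day before Visit 5 | Video call | No (fruit and vegetable inventory) |
| Visit 5 | Centre; exit survey, height, weight and BMI | No |

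A participant withdrawn after missing Visit 3 or 4 would normally have no primary outcome, although one could have been collected. A participant who misses only Visit 5 could already have one.

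**2. The plan's own figures.** Inputs from the Power analysis section: reductions of 331 g and 33 g, difference 298 g, SD of change 295 g. Effect size = 298/295 = 1.01. Alpha and sidedness are not stated. Two-sided 5% is assumed, and with a two-sample t-test it gives power 0.918 at 23 per group and 0.875 at 20 per group, matching the stated 0.92 and 0.88. One-sided 5% gives 0.958 and 0.932 and does not match. Attrition = 3/23 = 13.0%, as stated. The 0.88 figure therefore allows for fewer participants, but not for which participants are lost.

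**3. Illustration with a real effect.** Assumptions, none of them in the documents: k of 23 treatment households are withdrawn; their true change equals the control-arm change; those who remain show the planned 298 g; withdrawal does not shift the control mean; SD stays at 295 g.

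As-randomised difference = 298 × (23 − k)/23. Overstatement = 298 divided by that difference. Power is for all 23 per arm.

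| k | As-randomised difference | Effect size | Power at 23 per arm | Overstatement among those remaining |
|---|---|---|---|---|
| 2 | 298 × 21/23 = 272 g | 0.92 | 0.86 | 1.10 |
| 3 | 298 × 20/23 = 259 g | 0.88 | 0.83 | 1.15 |
| 5 | 298 × 18/23 = 233 g | 0.79 | 0.75 | 1.28 |

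**4. Illustration with no true effect.** Suppose k of 23 are lost from the treatment arm only, and their mean change is D standard deviations worse than that of the treatment households who remain. Spurious difference = (k/23) × D × 295 g.

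| k | D | Shift | Two-sided type I error (nominal 0.05) |
|---|---|---|---|
| 3 | 0.5 | 19 g | 0.055 |
| 3 | 1.0 | 38 g | 0.070 |
| 3 | 1.5 | 58 g | 0.096 |
| 5 | 0.5 | 32 g | 0.063 |
| 5 | 1.0 | 64 g | 0.103 |
| 5 | 1.5 | 96 g | 0.173 |

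If the loss is equal and similarly selective in both arms and there is no true effect, the expected shift is zero.

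**The case against.** A reader might infer that the protocol prescribes a completers-only analysis, that it removes the least engaged households, and that this favours the intervention. The documents support none of the three.

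- **Completers-only analysis.** The rule is permissive, and no section restricts the analysis to completers. The completer count and the 20 per group are sample-size statements. The risk comes from silence about the analysis set.
- **Data collection stopping.** The sentence that ends data collection is limited to voluntary withdrawal. It cannot be cited as proof that follow-up ends when staff withdraw someone; for that case the protocol says nothing.
- **Least engaged households.** Nothing describes who misses visits or why. The Procedures section offers Wednesday, Thursday or Friday attendance and home delivery in extenuating circumstances, and the schedule says timing is approximate. All of this should reduce missed visits.
- **Direction of bias.** Both arms receive boxes, and the control is matched on number, length, structure and content of sessions and on follow-up contacts. Large differences in attendance are therefore less likely. Matching does not, however, make the link between non-attendance and waste the same in both arms.
- **Size.** The plan's 13% is attrition from all causes, including voluntary dropout, which a change to this rule would not recover. It is not a rate for missed-visit withdrawals, and 5 of 23 (22%) is beyond any attrition the plan considers.

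These objections limit what can be claimed about direction and size. They do not answer the core point: the protocol permits removal for a post-randomisation behaviour when the outcome can still be measured, and it names no analysis set to contain the effect.

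**Conclusion.** The point holds in a limited form. The protocol allows discretionary withdrawal of randomised participants for missed visits that are not needed to measure the primary outcome, and it states neither an as-randomised analysis set nor a method for missing outcomes. The primary comparison may therefore default to those who kept attending. Bias would follow if non-attendance, or its link to food waste, differs by arm, or if treatment-arm non-attenders benefit less.

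The overstatement of about 10% to 28% (298 g against 272 to 233 g) is an illustration. It depends on 2 to 5 treatment-arm withdrawals under this rule and on those households showing only the control-arm change. The inflated type I error likewise needs one-sided, selective loss. Neither is a forecast. Confidence is moderate: the gap in the plan is clear, while the direction and size of its effect are not established.

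**What to change.** **Changes**

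1. In Withdrawal of Subjects, separate stopping the coaching visits from leaving follow-up, and state that missing Visit 3 or 4 does not end data collection.
2. Ask every randomised participant for the 3-day follow-up recording and the closing inventory unless they withdraw consent to data collection.
3. Define the primary analysis as all randomised participants in their assigned arm, regardless of attendance.
4. State a method for outcomes still missing, since voluntary withdrawals will leave some. One option is a likelihood-based model that includes baseline waste. The clean-out (Toss) records kept between the two full recording windows could inform it, though they do not cover preparation or eating waste.
5. Report the completers' comparison as a sensitivity analysis.

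Whether coaching or boxes continue for someone who misses visits stays the sponsor's decision.

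**Cost.** Some protocol wording and a few reminders through the app already in use. The Compensation section ties $165 to completing the remaining 21 days, so the sponsor should check that this condition does not deter non-attenders from recording. The estimate may become less favourable.
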